7.3.4 Calibration Exercise and Repeatability of Plaque Assessments by Evaluator

The dental examiners (evaluators) must have completed the standard calibration exercise and repeatability procedure on the QHT prior to the conduct of this study. The statistical report containing the results of this exercise and procedure will be written prior to conduct of the study and maintained on file as documentation that all evaluators can conduct the QHT scoring in a consistent manner and any differences between evaluators would be negligible.

7.4 Investigational Product

[Table 5](#) shows a description of the investigational product and the placebo to be used in this study. The active ingredient is KSL-W. The other materials contained in the product (CPC, an isomalt additive, peppermint powder, and sucralose) meet United States Pharmacopeia/National Formulary specifications and are listed on the Food and Drug Administration's (FDA) Inactive Ingredient Guide for oral formulations. Each tablet of gum is at the defined formulation. The placebo chewing gum will be identical in appearance and will differ only in the amount of active ingredient (KSL-W) and isomalt.

Table 5: Description of Investigational Product and Placebo

Product Name	Antiplaque Chewing Gum	Placebo
Dosage Form	Chewing gum	Chewing Gum
Unit Dose	30 mg	0 mg
Route of Administration	Oral	Oral
Physical Description	White to yellowish, round compressed tablet	White to yellowish, round compressed tablet
Manufacturer	Fertin Pharma	Fertin Pharma
Lot Number	3925-273	3925-267
Product Indication	Reduction of plaque and gingivitis	None

7.4.1 Investigational Product Packaging and Labeling

The APCG and placebo products are supplied in bulk. Each opaque plastic vial (Activ-Vial®) contains 20 pieces of gum and a desiccant. Each vial is labeled for human administration and includes the following statement: "Caution: New Drug – Limited by Federal (or U.S.) Law to Investigational Use." [Figure 2](#) and [Figure 3](#) display the representative vial labels for 30 mg KSL-W and Placebo, respectively.

Figure 2: Representative Bulk Antiplaque Chewing Gum Vial Label: KSL-W

Antiplaque Chewing Gum (APCG), 30 mg KSL-W, 20 pcs
Lot Number: 3925-273
Contains: 30 mg KSL-W Storage: 2-8°C
Caution: New Drug – Limited by Federal (or United States) law to investigational use.
MFG Date: 22Nov2012
Manufactured by: Fertin Pharma, Vejle, Denmark

Figure 3: Representative Bulk Antiplaque Chewing Gum Vial Label: Placebo

Antiplaque Chewing Gum (APCG), Placebo, 20 pcs
Lot Number: 3925-267
Contains: 0 mg KSL-W Storage: 2-8°C
Caution: New Drug – Limited by Federal (or United States) law to investigational use.
MFG Date: 19Nov2012
Manufactured by: Fertin Pharma, Vejle, Denmark

7.4.2 Investigational Product Storage

The study drug is manufactured in accordance with Good Manufacturing Practices (GMP) by Fertin Pharma. Fertin Pharma will ship the product to Salus Research under refrigeration (2-8°C or 35.6 - 46.4°F) in opaque plastic vials (Activ-Vial®). At the site, the gum will be stored at 2-8°C or 35.6 - 46.4°F. A Temperature log will be maintained at the site and checked during site visits by the sponsor's clinical study monitor.

The product may be removed from the temperature-controlled environment and maintained at room temperature conditions, defined as the prevailing temperature in a working area (approximately 20-25°C or 68-77°F), during certain periods during the study: preparation of dose administration at the clinical site, and packaging and storage for unsupervised doses while in the subjects' possession (unsupervised chews).

7.4.3 Investigational Product Preparation

Each of the APCG and placebo products will be provided as a ready-to-use piece of gum from the manufacturer. The product will be repackaged into a new vial for each subject. Each blinded vial will contain 14 pieces of gum, either active or placebo that will be prepared according to the randomization schedule in order to maintain the double-blind nature of the study. Preparation of the subject's vials with their assigned doses will be performed ahead of time at room temperature and then returned to refrigeration (2-8°C or 35.6 - 46.4°F) for storage until dispensed to the subject.

Approximately one (1) hour prior to dispensing, the subject's vial of blinded study product will be removed from refrigerated storage to allow time for the product to come to room temperature. For the first chew, the assigned study product will be dispensed to the subjects by designated study staff for supervised use at the site. For unsupervised use, enough investigational product will be dispensed to each subject for self-administration during the 4 day study period. Subjects

will be given 2 additional chewing gum tablets, to use if the product is inadvertently lost or misplaced. If the subject needs additional product (ie. more than 2 tablets) they will need to contact Salus Research. The subjects will be instructed on proper storage of the study product.

7.4.4 Investigational Product Accountability

The sponsor's representative is responsible for distributing the investigational product to the study site and has ultimate responsibility for accountability of study drug. The sponsor's representative has delegated the drug accountability responsibility for this product to the Principal Investigator. The Principal Investigator may delegate in writing this responsibility to another individual, but the Principal Investigator is ultimately responsible for the investigational product and its proper storage from the time the investigational product arrives at the study site until it is returned to the sponsor's representative or designee or is destroyed, as directed by the sponsor's representative. Drug accountability will be conducted once the site receives the investigational product. The Principal Investigator or designee, will maintain logs of storage, drug accountability by subject, including dispensed product, and product remaining before final disposition within Salus Research. In the event of a temperature excursion, the Principal Investigator should contact the Sponsor Representative, who will make the determination of the product's integrity and use.

Used investigational product will be collected by study staff during the supervised time (first chew) at the site on Day 0. For each of the unsupervised doses, subjects will be instructed to collect the used product in individually labeled bags ([Figure 4](#)) and return them to the site at Visit 3 (Day 4). A total of 11 bags of used investigational product will be returned at Visit 3. If a subject forgets to return the used product, they will be asked to make arrangements to return the used product bags to the site. Subjects will also be instructed to return any unused product resulting from missed doses. Unreturned used and unused product (missed dose) will be considered protocol deviations.

Used product and unused product will be verified by the sponsor's study monitor and then destroyed in accordance with site SOPs for destruction of study drug as directed by the sponsor's representative and as stipulated by institutional, state, and Federal regulations.

Figure 4: Example Label for Used Product Bags

Subject Number:

Date and Time of Chew:

Caution: New Drug - Limited by Federal (or United States) law to investigational use.

Distributed by Salus Research

Phenylketonurics: Contains Phenylalanine

KEEP OUT OF REACH OF CHILDREN

7.5 Duration of Subject Participation

Each subject will participate for up to 21 days; screening, 4 days of treatment followed by 1 day for dental evaluation and end of study activities.

7.6 Dose-adjustment Criteria

For this study, dose adjustments will not be made other than to discontinue the use of study medication if the situation warrants.

7.6.1 Safety Criteria for Dose Adjustment or Stopping Doses

This section is not applicable.

7.6.2 Pharmacokinetic Criteria for Dose Adjustment or Stopping Doses

This section is not applicable.

7.6.3 Study Termination Criteria

The Principal Investigator, research monitor, sponsor's representative, the IRB and/or the United States Army Medical Research and Material Command (USAMRMC) Office of Research Protections, Human Research Protection Office or the FDA may stop or suspend the use of this product at any time.

7.7 Trial Treatment Randomization Codes

Subject ID numbers will be assigned in ascending numerical order as each subject signs the consent form. The Subject ID numbers will be assigned from one centrally located pre-printed list.

Each subject who meets the inclusion and exclusion criteria and is deemed fully eligible will be assigned a unique randomization number. The randomization numbers will be on the randomization list, generated by the independent unblinded biostatistician. The randomization numbers will be assigned to subjects sequentially as they are randomized at Visit 2.

7.8 Identification of Data to be Recorded on the Case Report Forms

All eCRF data will be transcribed from subject's source records. For more information on data handling, refer to [section 16](#).

8 Selection and Withdrawal of Subjects

8.1 Recruitment of Subjects

Salus Research is located in Fort Wayne, Indiana. Salus Research expects to recruit from a subject population in the surrounding Fort Wayne area. Based on the site's vast experience with dental trials and database of potential participants, it is estimated that 35 subjects will need to be screened in order to obtain 26 subjects eligible for randomization.

The staff at Salus Research will be trained on the details of the protocol and will have the responsibility to identify potential study participants. A recruitment plan based on the inclusion/exclusion criteria of the study will be developed and submitted to the U.S. Investigational Review Board for approval. Salus Research will recruit subjects from their Salus Research Categorized Database of past study participants. After the IRB has approved the protocol and the study initiation visit has been completed, prospective subjects will be contacted by the study staff via telephone. These prospective subjects will be provided the study dates and, if interested, the inclusion and exclusion criteria from the protocol will be reviewed. Once this is complete and they are still interested, they will be scheduled for the Screening Visit.

8.2 Eligibility Screening

Each subject must satisfy all inclusion and exclusion criteria. During screening, the following assessments will be conducted: physical examination, urine drug screen, medical history, periodontal examination, OHT and OST examinations, oral hygiene check, plaque index measurement and vital sign measurements. Females of child-bearing potential must have a negative urine pregnancy test result at screening (14 \pm 2 days prior to randomization) in order to participate and must agree to use a reliable form of birth control throughout the duration of the study. The Principal Investigator or designee will make the final decision regarding the eligibility of the subject. Only eligible subjects will be given the investigational product.

8.2.1 Subject Inclusion Criteria

Subjects must meet all of the following criteria to be included in the study:

- I01 Males or females between 18 and 64 years of age (inclusive at time of screening)
- I02 A negative urine pregnancy test (females of childbearing potential only)
- I03 A negative urine drug test
- I04 On a reliable form of birth control for at least 30 days prior to the start of the study and willing to use a reliable form of contraception for the duration of the study (Females of childbearing potential only), with reliable contraception defined as:
 - Abstinence which has been the customary lifestyle of choice
 - Oral contraceptive, either estrogen/progesterone combined, or progesterone alone

- Injectable progesterone
- Implants of levonorgestrel
- Estrogenic vaginal ring
- Percutaneous contraceptive patches
- Intrauterine device or intrauterine system
- Double barrier method [condom or occlusive cap (diaphragm or cervical vault caps) plus spermicidal agent (foam, gel, film, cream, suppository)]
- Male partner sterilization at least 6 months prior to the female subject's entry into the study, and this male is the sole partner for that subject
- Post-menopausal for at least two years

I05 Good health, as determined by pertinent medical history, physical examination, and vital signs.

I06 A minimum of 20 natural teeth with 6 scorable surfaces per tooth

- Sufficient number of opposing posterior teeth to chew on both sides of the mouth as determined by the examining dentist
- Teeth that have gross caries, full crowns or extensive restorations on facial and/or lingual surfaces, orthodontic bands, and third molars are not included in the tooth count

I07 Subject must have refrained from all oral hygiene procedures 12 to 16 hours prior to screening visit.

I08 Plaque Index of 1.95 or greater (Turesky et al-1970)

I09 Willing to forgo any optional dental procedures during the study period, such as dental prophylaxis or teeth whitening.

I10 Ability to comprehend and a willingness to sign an informed consent, which includes the Authorization for the Release of Health Information document.

I11 Ability to access the internet to complete the drug compliance information

I12 Willingness to comply with all study procedures

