5.6 Known and Potential Risks and Benefits to Human Subjects

5.6.1 Risks/Discomfort to Subjects and Precautions to Minimize Risk

Outlined below are anticipated and unexpected adverse reactions, and a brief description of procedures to ameliorate risks and symptoms. All known risks and precautions described here are explained in detail in the informed consent.

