5.6.1.3 Pregnancy

Risks to unborn babies are unknown at this time. Pregnant females will be excluded from this study. Female subjects should not become pregnant for at least 3 months after receiving the last dose of investigational product. Male subjects should not have unprotected sex for at least 3 months after receiving the last dose of investigational product.

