15.3 Written Informed Consent

The informed consent process and document will be reviewed and approved by US Investigational Review Board, USAMRMC ORP and Sponsor's representative prior to initiation of the study. The consent document contains a full explanation of the possible risks, advantages, and alternate treatment options, and availability of treatment in the case of injury, in accordance with the United States Code of Federal Regulation, Title 21, Part 50 (21 CFR 50). The consent document indicates that by signature, the subject permits witnessing of applicable study procedures by the sponsor's representative, as well as access to relevant medical records by the sponsor's representative and by representatives of the FDA. The sponsor's representative will submit a copy of the initial IRB and sponsor's representative-approved consent form to the FDA

and will maintain copies of revised consent documents that have been reviewed and approved by US Investigational Review Board and ORP.

A written informed consent document, in compliance with 21 CFR Part 50, 32 CFR Part 219, and the Belmont Principles and HIPAA Authorization will be signed by the subject before any study-related procedures are initiated for that subject. This consent document must be retained by the investigator as part of the study records. Each subject will receive a copy of the signed informed consent document. The investigators or their designees will present the protocol in lay terms to individual subjects. Questions on the purpose of the protocol, protocol procedures, and risks to the subjects will then be solicited. Any question that cannot be answered will be referred to the PI. No subject should grant consent until questions have been answered to his/her satisfaction. The subject should understand that the study product is an investigational drug and is not licensed by the FDA for commercial use, but is permitted to be used in this clinical research. Informed consent includes the principle that it is critical the subject be informed about the principal potential risks and benefits. This information will allow the subject to make a personal risk versus benefit decision and understand the following:

- Participation is entirely voluntary,
- Subjects may withdraw from participation at any time,
- Refusal to participate involves no penalty, and
- The individual is free to ask any questions that will allow him/her to understand the nature of the protocol.

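### The contraception entry rule (section 8.2 and I04) is shorter and narrower than the 3-month precaution for both sexes in section 5.6.1.3

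*Protocol*

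**What the plan says.** The risk section and the eligibility section of the protocol set different rules.

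- **Section 5.6.1.3 (Pregnancy)** starts from "Risks to unborn babies are unknown at this time". It then sets two precautions: "Female subjects should not become pregnant for at least 3 months after receiving the last dose of investigational product" and, with the same starting point, "Male subjects should not have unprotected sex for at least 3 months".
- **Section 8.2 (Eligibility Screening)** says that females of childbearing potential "must agree to use a reliable form of birth control throughout the duration of the study". It puts no such duty on men.
- **Section 8.2.1, I04** asks for reliable birth control for at least 30 days before the study and, looking forward, that the subject be "willing to use a reliable form of contraception for the duration of the study (Females of childbearing potential only").

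Three other provisions bear on how the 3-month precaution could reach a subject. The introduction to section 5.6.1 states: "All known risks and precautions described here are explained in detail in the informed consent". Criterion I10 requires "Ability to comprehend and a willingness to sign an informed consent". Section 15.3 says the consent document "will be signed by the subject before any study-related procedures are initiated for that subject".

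**The concern.** The sponsor has judged that precautions are needed for 3 months in both sexes, yet the test for entry asks for less. As the criteria stand, a woman who plans to conceive in the week after discharge meets I04. A man who is unwilling to use protection meets every contraception criterion, because none applies to him.

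The criteria decide enrolment (section 9.1.1). They are also reviewed with prospective subjects by telephone before the screening visit (section 8.1). A prospect may thus hear a female-only rule for the length of the study and, if the consent form follows 5.6.1.3, meet a longer rule for both sexes at signing. If the consent form follows I04 instead, the 3-month precaution is lost. What is at stake is the avoidance of fetal exposure, not the trial's inference.

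**Working it through.** There is no sample size or power figure to reproduce. The check is a comparison of the texts with some counting of days.

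**1. Rules side by side**

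| Place | Who | Forward period |
|---|---|---|
| 5.6.1.3 | Female subjects | At least 3 months after last dose |
| 5.6.1.3 | Male subjects | At least 3 months after last dose |
| 8.2 | Females of childbearing potential | Study duration |
| I04 | Females of childbearing potential | Study duration |

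**2. End of the study relative to the last dose.** Dosing runs over Days 0 to 3 (section 7.2, Table 3), and discharge is at the Day 4 visit (section 9.1.4). Time in the study after the last dose is 4 − 3 = 1 day. As a cross-check on the end point, screening on Days −16 to −1 (16 days) plus Days 0 to 4 (5 days) gives 21 days, which agrees with section 7.5. The SAP event schedule has a different screening window but also ends on Day 4.

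**3. Uncovered period.** Assume that the study duration ends on Day 4 and that 3 months is 89 to 92 days, depending on the calendar. The precaution then runs to Day 3 + 89 = Day 92 at the earliest and Day 3 + 92 = Day 95 at the latest. The part outside the I04 commitment for women is 92 − 4 = 88 to 95 − 4 = 91 days. For men, the numbered criteria cover none of the period.

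**4. Count over all criteria.** I01 to I12 give 12 and E01 to E019 give 19, so 12 + 19 = 31.

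- On reproduction: 3 (I02 pregnancy test, I04 contraception, E017 pregnancy or breast-feeding).
- Asking for contraception: 1 (I04).
- Extending contraception past the study: 0.
- Asking contraception of male subjects: 0. The sterilized male in I04 is the partner of a female subject.

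**5. Whether another provision fills the gap.** I12 and E019 are general compliance criteria and do not clearly reach conduct after discharge. Section 5.9 mentions contraceptives but gives no period and no duty for men. The last pregnancy test is on Day 4, and no later contact is scheduled. Following pregnancies to term (section 11.5.2.1) and the SAP's provision for maternal and paternal events (section 7.1.1) are reporting, not prevention.

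**The case against.** The strongest reply is that the protocol names its own route for the precaution. Section 5.6.1 says that its precautions are explained in the consent form, the form is signed before any procedure, and willingness to sign is itself criterion I10. That route reaches both sexes, and without the form nobody can say that it fails. This stands, and it is why the finding stops at an inconsistency. But being told of a precaution is not an entry test, and only the criteria are checked one by one at screening and Day 0 (SAP listing LREF02.a).

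A second reply is that the two texts can both be obeyed and that, with no visit after Day 4, a 3-month criterion would record stated willingness only. That is true, but I04 already records stated willingness; it does so for too short a period and for one sex.

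A third reply is that the risk is small. KSL-W degrades rapidly, its systemic exposure is expected to be very low, and with CPC it was not genotoxic (section 5.5.1). CPC was absorbed in the animal studies, but these used gavage dosing, and section 7.4 says that CPC meets compendial specifications and is on FDA's inactive ingredient list for oral products. Section 5.5.1 lists no reproductive study, but it covers work by or through one laboratory, so others may exist. Several I04 methods, such as an implant or intrauterine device, would normally continue after Day 4. Only 13 subjects are planned to receive KSL-W, although blinding means the rule must apply to all 26. These points keep the severity low. They do not remove the mismatch, because the sponsor itself calls the risk to unborn babies unknown.

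Finally, I04 also requires 30 days of contraception before the study. The gap concerns the forward commitment only.

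**Conclusion.** The concern holds. The forward contraception commitment in section 8.2 and I04 covers about 1 day of the period of at least 3 months in section 5.6.1.3 for women of childbearing potential, and none of it for men. This rests on the study ending at discharge on Day 4; the mismatch for men does not depend on that reading.

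At most 26 subjects are concerned; the split by sex is not given. How many would lack the 3-month instruction cannot be estimated without the consent form. Confidence is high that the texts differ. Nothing is claimed about actual harm or about what subjects were told. This is a modest subject-safety point worth correcting.

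**What to change.** 1. In section 8.2 and I04, extend the forward period to the duration of the study and at least 3 months after the last dose.
2. Add an inclusion criterion for men: willing to avoid unprotected sex during the study and for at least 3 months after the last dose.
3. Check that the consent form gives the same period for both sexes.

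Section 5.6.1.3 can stay as it is. Shortening it would also reconcile the text, but the sponsor would have to argue for a shorter period, and the protocol gives no such argument.

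Optionally, the 3-month agreement not to breast-feed in section 5.6.1.4 could become a criterion. It would matter only for a lactating woman who has stopped nursing, since E017 already excludes breast-feeding women.

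The cost is two edited sentences, one new criterion and a slightly stricter entry condition. Visits, sample size and analysis do not change.
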